### 11.5.2. Vital Signs

Oral temperature, pulse rate, respiratory rate, and blood pressure will be assessed

Blood pressure and pulse measurements will be assessed with a completely automated device. Manual techniques will be used only if an automated device is not available.

Blood pressure and pulse measurements should be preceded by at least 5 minutes of rest for the subject in a quiet setting without distractions (e.g., television, cell phones).

Vital signs (to be taken before blood collection for laboratory tests) will consist of 1 pulse and 3 blood pressure measurements (3 consecutive blood pressure readings will be recorded at intervals of at least 1 minute). The 3 blood pressure readings will be recorded on the CRF.

## 11.5.3. Electrocardiograms

Triplicate 12-lead ECGs will be obtained as outlined in Schedule of Events, using an ECG machine that automatically calculates the heart rate and measures PR, QRS, QT.

At each time point at which triplicate ECG are required, 3 individual ECG tracings should be obtained as closely as possible in succession, but no more than 2 minutes apart.

## 11.5.4. Clinical Safety Laboratory Assessments

The following clinical laboratory tests will be performed at the timepoints designated in the schedule of events.

- Hematology: WBC and differential count, RBC, Hgb, Hct, MCV, MCH, HCHC, RDW, MPV, Platelets
- o Biochemistry: Sodium, Potassium, Bicarbonate or CO2, Chloride, Total Bilirubin, Creatinine, BUN, Calcium, Alkaline Phosphatase, ALT, AST, Total Protein, Albumin, eGFR, Globulin
- Coagulation as per Study Reference Manual
- o Urinalysis as per Study Reference Manual
- Hemoglobin A1c (HbA1c) to be collected at Visit 1 only

All laboratory tests required above will be performed by the central lab. Local laboratory results are only permitted in the case of a medical emergency or if the central laboratory results are not available in time

for either study treatment administration and/or response evaluation. Additional tests may be performed at any time during the study as determined necessary by the Investigator or required by local regulations. If a local sample is required in the case of an emergency, it is important that the sample for central analysis is obtained at the same time. Additionally, if the local laboratory results are used to make either a study treatment decision or response evaluation, the results must be entered into the CRF

The investigator must review the laboratory report, document this review, and record any clinically relevant changes occurring during the study in the AE section of the CRF. The laboratory reports must be filed with the source documents. Clinically significant abnormal laboratory findings are those which are not associated with the underlying disease, unless judged by the investigator to be more severe than expected for the subject's condition.

Study subjects who have laboratory tests with values considered clinically significantly abnormal and designated as an AE during the study, should have repeat labs drawn after the last dose of study treatment and should continue repeat labs until the values return to normal or baseline or are no longer considered clinically significant by the investigator or medical monitor.

# 12. STATISTICAL CONSIDERATIONS

# **12.1.** Sample Size Determination

This is a pilot dose-ranging study. No sample size calculations were conducted.

# 12.2. Population for Analysis

All statistical processing will be performed using SAS® unless otherwise stated. All subjects enrolled in the study that were dispensed and applied test article at least once will be included in the analysis and will be considered in the intent-to-treat (ITT) population.

# 12.3. Statistical Analysis

The statistical analysis plan will be developed and finalized before database lock and will describe the subject populations to be included in the analyses, and procedures for accounting for missing, unused, and spurious data. This section is a summary of the planned statistical analyses of the primary and secondary endpoints.

# 12.3.1. Efficacy Analysis

Efficacy data including clinical and microbiological response will be summarized by dose group and will include analysis further defined in the statistical analysis plan.

# 12.3.2. Safety Analysis

Adverse Events: Treatment-emergent adverse events will be coded according to the Medical Dictionary for Regulatory Activities (MedDRA). The incidence of treatment-emergent adverse events will be summarized by body system and preferred term

## 12.3.3. Interim Analysis

A safety review by an independent DMC will be conducted after each cohort to confirm it is acceptable to proceed to the next dose level.

# 12.3.4. Parameters Requiring Pause in Treatment

Individual: wound gangrene; osteomyelitis; G3-4 AE; SAE related to study drug.

**Cohort**: ≥3 of the above individual criteria in any given cohort

# 13. STUDY GOVERNANCE CONSIDERATIONS

Study Governance considerations are provided in Appendix 3, including:

- Regulatory and ethical considerations
- Financial disclosure
- Informed consent process
- Committee structure

# APPENDIX 1. GUIDANCE AND COLLECTION OF PREGNANCY INFORMATION

#### **Definitions**

#### Women of Childbearing Potential (WOCBP)

A women is considered fertile following menarche and until becoming post-menopausal unless permanently sterile (see below).

# Women in the following categories are not considered WOCBP

- 1. Premenarchal: premenopausal female with 1 of the following:
  - Document hysterectomy
  - Documented bilateral salpingectomy
  - Documented bilateral oophorectomy

Note: Documentation can come from the site personnel's: review of the subject's medical records, medical examination, or medical history interview.

- 2. Postmenopausal female:
  - A postmenopausal state is defined as no menses for 12 months without an alternative medical cause.
  - Females on HRT and whose menopausal status is in doubt will be required to use one of the non-hormonal highly effective contraception methods if they wish to continue their HRT during the study. Otherwise, they must discontinue HRT to allow confirmation of postmenopausal status before study enrollment.

# **Contraception Guidance**

## **Male Subjects**

Are abstinent from penile-vaginal intercourse as their usual and preferred lifestyle (abstinent on a long term and persistent basis) and agree to remain abstinent.

Men with a pregnant or breastfeeding partner must agree to remain abstinent from penile-vaginal intercourse or use a male condom during each episode of penile penetration during trial participation and for one month following trial completion.

Refrain from donating sperm for the duration of the study and for one month after study completion or the last dose of study treatment.

## **Female Subjects**

#### Highly Effective Contraceptive Methods That Are User Dependent(a)

Failure rate <1% per year when used consistently and correctly.

Combined (estrogen and progestogen containing) hormonal contraception associated with inhibition of ovulation.)

- Oral
- Intravaginal
- Transdermal

Progestogen only hormonal contraception associated with inhibition of ovulation

- Oral
- Injectable

# **Highly Effective Methods That Are User Independent**

Implantable progestogen only hormonal contraception associated with inhibition of ovulation

- Intrauterine device (IUD)
- Intrauterine hormone-releasing system (IUS)
- Bilateral tubal occlusion

#### Vasectomized Partner

A vasectomized partner is a highly effective contraception method provided that the partner is the sole male sexual partner of the WOCBP and the absence of sperm has been confirmed. If not, an additional highly effective method of contraception should be used.

#### **Sexual Abstinence**

Sexual abstinence is considered a highly effective method only if defined as refraining from heterosexual intercourse during the entire period of risk associated with the study treatment.

- (a): Typical use failure rates may differ from those when used consistently and correctly. Use should be consistent with local regulations regarding the use of contraceptive methods for subjects participating in clinical studies.
- (b): Hormonal contraception may be susceptible to interaction with the study treatment, which may reduce the efficacy of the contraceptive method. In this case, two highly effective methods of contraception should be utilized during the treatment period and for at least 30 days after the last dose of study treatment.

# **Pregnancy Testing**

- Serum and urine pregnancy testing will occur per the Schedule of Events.
- WOCBP should only be included after a confirmed menstrual period and a negative highly sensitive serum pregnancy test.
- A final serum pregnancy test will occur at the EOS/ET visit and at the safety follow-up safety visit at week 42 which occurs 14 days (+ or 2 days) after last dose of study treatment.

# Male Subjects with Partners who Become Pregnant

• The investigator will attempt to collect pregnancy information on any male subject's female partner who becomes pregnant while the male subject is in this study.

• After obtaining the necessary signed informed consent from the pregnant female partner directly, the investigator will record pregnancy information on the appropriate form and submit it to the sponsor within 24 hours of learning of the partner's pregnancy. The female partner will also be followed to determine the outcome of the pregnancy. Information on the status of the mother and child will be forwarded to the sponsor. Generally, the follow-up will be no longer than 6 to 8 weeks following the estimated delivery date. Any termination of the pregnancy will be reported regardless of fetal status (presence or absence of anomalies) or indication for the procedure.

# Female Subjects who Become Pregnant

- The investigator will collect pregnancy information on any female subject who becomes pregnant while participating in this study. Information will be recorded on the appropriate form and submitted to the sponsor within 24 hours of learning of a subject's pregnancy. The subject will be followed to determine the outcome of the pregnancy. The investigator will collect follow-up information on the subject and the neonate and the information will be forwarded to the sponsor. Generally, follow-up will not be required for longer than 8 weeks beyond the estimated delivery date. Any termination of pregnancy will be reported, regardless of fetal status (presence or absence of anomalies) or indication for the procedure.
- While pregnancy itself is not considered to be an AE or SAE, any pregnancy complication or elective termination of a pregnancy will be reported as an AE or SAE. A spontaneous abortion is always considered to be an SAE and will be reported as such. Any post-study pregnancy related SAE considered reasonably related to the study treatment by the investigator will be reported to the sponsor as described in Appendix 1. While the investigator is not obligated to actively seek this information in former study subjects, he or she may learn of an SAE through spontaneous reporting.
- Any female subject who becomes pregnant while participating in the study will discontinue study treatment and be withdrawn from the study but will be followed for 8 weeks post-delivery.

# APPENDIX 2: ADVERSE EVENTS DEFINITIONS AND PROCEDURES FOR RECORDING, EVALUATING, FOLLOW-UP, AND REPORTING

#### **Definition of AE**

An AE is any untoward medical occurrence in a subject or clinical study subject, temporally
associated with the use of study treatment, whether or not considered related to the study
treatment.

Note: An AE can therefore be any unfavorable and unintended sign (including an abnormal laboratory finding), symptom, or disease (new or exacerbated) temporally associated with the use of study treatment. Local reactions to test product administration include but are not limited to pain, edema, rash, cellulitis, localized infectious processes, and any systemic reaction including fever, allergic reaction, and anaphylaxis, and would be considered to be AEs.

# **Events Meeting the AE Definition**

- Any abnormal laboratory test results (hematology, clinical chemistry, or urinalysis) or other safety assessments (e.g., ECG, radiological scans, vital signs measurements), including those that worsen from baseline, considered clinically significant in the medical and scientific judgment of the investigator (i.e., not related to progression of underlying disease).
- Exacerbation of a chronic or intermittent pre-existing condition including either an increase in frequency and/or intensity of the condition.
- New conditions detected or diagnosed after study treatment administration even though it may have been present before the start of the study.
- Signs, symptoms, or the clinical sequelae of a suspected drug-drug interaction.
- Signs, symptoms, or the clinical sequelae of a suspected overdose of either study treatment or a concomitant medication. Overdose per se will not be reported as an AE/SAE unless it is an intentional overdose taken with possible suicidal/self-harming intent. Such overdoses should be reported regardless of sequelae.
- "Lack of efficacy" or "failure of expected pharmacological action" per se will not be reported as an AE or SAE. Such instances will be captured in the efficacy assessments. However, the signs, symptoms, and/or clinical sequelae resulting from lack of efficacy will be reported as AE or SAE if they fulfil the definition of an AE or SAE.

# **Events NOT Meeting the AE Definition**

- Any clinically significant abnormal laboratory findings or other abnormal safety assessments which in the opinion of the Investigator are associated with the underlying disease, unless judged by the investigator to be more severe than expected for the subject's condition.
- The disease/disorder being studied or expected progression, signs, or symptoms of the disease/disorder being studied, unless more severe than expected for the subject's condition.
- Medical or surgical procedure (e.g., endoscopy, appendectomy): the condition that leads to the procedure is the AE.

- Situations in which an untoward medical occurrence did not occur (social and/or convenience admission to a hospital).
- Anticipated day-to-day fluctuations of pre-existing disease(s) or condition(s) present or detected at the start of the study that do not worsen.

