#### **Definition of SAE**

If an event is not an AE per definition above, then it cannot be an SAE even if serious conditions are met (e.g., hospitalization for signs/symptoms of the disease under study, death due to progression of disease).

An SAE is defined as any untoward medical occurrence that, at any dose:

- Results in Death
  - O The term 'life-threatening' in the definition of 'serious' refers to an event in which the subject was at risk of death at the time of the event. It does not refer to an event, which hypothetically might have caused death, if it were more severe.
- Requires in subject hospitalization or prolongation of existing hospitalization
  - o In general, hospitalization signifies that the subject has been detained (usually involving at least an overnight stay) at the hospital or emergency ward for observation and/or treatment that would not have been appropriate in the physician's office or ambulatory care setting. Complications that occur during hospitalization are AEs. If a complication prolongs hospitalization or fulfills any other serious criteria, the event is serious. When in doubt as to whether "hospitalization" occurred or was necessary, the AE should be considered serious. Hospitalization for elective treatment of a pre-existing condition that did not worsen from baseline is not considered an AE.
- Results in persistent disability/incapacity
  - The term disability means a substantial disruption of a person's ability to conduct normal life functions.
  - This definition is not intended to include experiences of relatively minor medical significance such as uncomplicated headache, nausea, vomiting, diarrhea, influenza, and accidental trauma (e.g., sprained ankle) which may interfere with or prevent everyday life functions but do not constitute a substantial disruption.
- Is a congenital anomaly/birth defect
- Other situations:

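### An undefined filter for expected progression of the ulcer lets some target-ulcer worsening escape AE and SAE counts, and the SAP safety section has no wound table to catch it

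*Protocol*

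**What the plan says.** **Definition of AE (Protocol Appendix 2).** An AE is any untoward occurrence associated in time with study treatment, related or not, and includes new or worsened disease. The note adds: "Local reactions to test product administration include but are not limited to pain, edema, rash, cellulitis, localized infectious processes", and classes these reactions as AEs.

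**Events Meeting the AE Definition.** These include "Exacerbation of a chronic or intermittent pre-existing condition including either an increase in frequency and/or intensity of the condition". Failure to work is not itself an AE, but "the signs, symptoms, and/or clinical sequelae resulting from lack of efficacy will be reported as AE or SAE if they fulfil the definition".

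**Events NOT Meeting the AE Definition.** The list includes "The disease/disorder being studied or expected progression, signs, or symptoms of the disease/disorder being studied", followed by the exception "unless more severe than expected for the subject's condition".

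**Definition of SAE.** "If an event is not an AE per definition above, then it cannot be an SAE even if serious conditions are met". The examples given are "hospitalization for signs/symptoms of the disease under study, death due to progression of disease".

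**Pause criteria (Protocol 12.3.4).** Treatment of a subject pauses for "wound gangrene; osteomyelitis; G3-4 AE; SAE related to study drug". Three or more of these in a cohort pause the cohort.

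**Endpoint and analysis.** Protocol section 4 lists local wound and skin assessments among the primary safety variables. The SAP (*Analysis*) makes TEAE incidence the primary analysis. Its other safety outputs are laboratory values, vital signs and physical examination changes. Ulcer area appears only as percentage area reduction (PAR), under efficacy.

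**The concern.** The gel is applied to the ulcer, so local harm could look like the ulcer getting worse. That is the class of event to which the expected-progression filter applies. The filter works before any count is made. An event judged expected is not an AE, so it cannot be a TEAE, a grade 3-4 AE or an SAE. With no definition of expected, two investigators could classify the same event differently and both be following the protocol.

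At stake is how complete the primary safety summary is, and how complete the AE and SAE record is that the DMC uses when it decides on escalation. Each lost event is large at this sample size: 1/12 = 8.3 percentage points for a dose group and 1/8 = 12.5 points for pooled placebo.

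**Working it through.** **1. One event traced through the plan.** Take a target-ulcer infection after first application that leads to hospitalization.

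| Text | Result |
|---|---|
| Appendix 2, Definition of AE | AE, related or not; localized infection is named as a local reaction |
| Appendix 2, Events Meeting | AE, if seen as exacerbation of the existing ulcer |
| Appendix 2, Events NOT Meeting | Not an AE, if judged expected for this subject |
| Appendix 2, Definition of SAE | If not an AE, not an SAE despite hospitalization |
| Protocol 12.3.4 | If not an AE, neither AE-dependent criterion is met |
| SAP, primary analysis | If not an AE, not in TEAE incidence |

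Rows two and three can both apply, and no rule says which prevails. Judging such an infection expected is not far-fetched, because Protocol 3.1 itself describes these ulcers as prone to becoming infected again. The lack-of-efficacy rule does not settle it, since it requires the event to meet the AE definition and so leads back to row three. Procedures are not AEs either; the condition behind them is. If that condition were judged expected, an amputation would surface only as an unhealed outcome (SAP, *Missing data*).

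**2. Is it caught elsewhere in the safety section?** The SAP has no local wound or skin table. The physical examination is scheduled only at Visits 1 and 8 and at early termination (Protocol section 9), and skin is not in its minimum list of systems (11.5.1). PAR = ((A1 − A2)/A1) × 100 is negative when the ulcer enlarges (A2 > A1). It is summarized by week and group as efficacy, which does not count the subjects whose ulcer grew, and missing values are carried forward.

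**3. Size.** The protocol made no sample size calculation and gives no event rates, so there is no plan figure to reproduce. The rates p and capture fractions s below are assumptions. With n subjects, the number with a recorded event is binomial (n, p × s), and

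P(at least 3) = 1 − Σ(k = 0 to 2) C(n, k)(ps)^k (1 − ps)^(n − k).

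The row n = 12 is the active arm of a cohort. The row n = 16 is the whole cohort, with the same rate assumed on placebo.

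| n | True rate | All recorded | 75% recorded | 50% recorded |
|---|---|---|---|---|
| 12 | 10% | 0.111 | 0.056 | 0.020 |
| 12 | 20% | 0.442 | 0.264 | 0.111 |
| 12 | 30% | 0.747 | 0.528 | 0.264 |
| 16 | 10% | 0.211 | 0.113 | 0.043 |
| 16 | 20% | 0.648 | 0.439 | 0.211 |
| 16 | 30% | 0.901 | 0.733 | 0.439 |

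These figures apply only to criteria that depend on AE or SAE status.

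**4. What an empty table would mean.** With zero recorded events, the one-sided 95% upper bound is 1 − 0.05^(1/n): 22.1% for n = 12 and 11.7% for n = 24. If only half of events are recorded, the bound on the true rate doubles, to 0.221/0.5 = 44.2% and 0.1173/0.5 = 23.5%.

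**The case against.** A reader might infer that the primary endpoint is blind to the harms a wound gel would cause. The documents do not support that.

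- **The exclusion is not blanket.** Worsening beyond expectation is an AE and can become an SAE. Local reactions, exacerbations and newly diagnosed conditions are also AEs.
- **Gangrene and osteomyelitis are poor examples of expected progression.** Entry requires a Wagner grade 1 ulcer, adequate perfusion and no suspected bone infection. On the protocol's own scale osteomyelitis is grade 3 and gangrene grades 4 to 5. Both count toward a pause by name, whatever their AE status.
- **The filter does not ask for a causality judgment.** It compares severity with expectation. Relatedness is graded separately on five levels (Appendix 2, *Assessment of Causality*).
- **Enlargement is measured.** The schedule lists imaging and visual examination at every visit.
- **It cannot be said that a signal would vanish.** For an invented 3/12 versus 1/8, the Fisher two-sided p is about 0.62 with full recording. Halving both arms (1.5/12 versus 0.5/8) leaves the ratio at 2. No safety hypothesis is tested, and blinding means no difference between arms is built in.

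All of this stands, and it narrows the point. It does not define expected, say which rule prevails when exacerbation and expected progression both apply, or lift the SAE bar. Nor does it put wound findings in the safety section. Naming gangrene and osteomyelitis secures the pause, not the TEAE or SAE count.

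**Conclusion.** The point holds as a gap in recording and reporting. Target-ulcer worsening that an investigator judges expected can be left out of TEAE incidence, out of SAE status even with hospitalization, and out of the two pause criteria that depend on that status. The grade 3-4 criterion is the more exposed of the two, since an event judged expected progression is unlikely also to be judged drug-related.

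The text conflict is certain. The size is not: it depends on how often worsening occurs and how often it is called expected, and the documents give neither. Under the assumed rates of 10% to 30% in 12 active subjects, half capture lowers the chance of at least three recorded events from 0.111-0.747 to 0.020-0.264. The likely effect is undercounting in all arms, not bias between them. The dose-limiting toxicity criteria are in the DMC charter, which is not among the documents, so whether escalation itself depends on AE status is unknown. This is a cheap improvement, not a fault that invalidates the design.

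**What to change.** 1. **Reconcile the four Appendix 2 sections on AE and SAE definition.** State that discrete target-ulcer complications after first application (infection, gangrene, osteomyelitis, amputation, hospitalization for the ulcer) are always recorded as AEs, and as SAEs when a serious criterion is met, regardless of expectedness. Keep the existing relatedness grading.
2. **Remove hospitalization for the disease under study** from the examples of events that cannot be SAEs.
3. **Add by-group tables to the SAP safety section** for local wound and skin findings and for ulcer enlargement (number and percentage of subjects with negative PAR at each visit).
4. **Do not make every area increase an AE.** Imaging generally follows debridement, and Appendix 4 allows light debridement back to adherent skin at the ulcer edge. That can itself enlarge the measured area and would fill the AE table with procedural noise.

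The cost is a wording amendment and two tables. Somewhat more AEs and SAEs will be recorded in all arms, some of them background disease. Treatment, visits and sample size do not change.
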